5.4.1 Enrollment of Medicare Beneficiaries

This clinical investigation will enroll both Medicare beneficiaries and private payors in the US. Because this study enrolls Medicare beneficiaries, it conforms to all standards of Medicare coverage requirements. The Risks and Benefits in section 15 of this CIP describe how all enrolled subjects, including Medicare beneficiaries, may be affected by the hypothesis under investigation. The demographics representative of LVAD therapy reflect primarily a CMS population. Common complications associated with LVADs are frequently associated with hemocompatibility-related adverse events such as pump thrombosis, stroke and bleeding events. Improvements in contemporary LVAD technology with the HeartMate 3 LVAD have shown significant improvement in reduction of pump

Clinical Investigation Plan

thrombosis, stroke and bleeding, but bleeding events persist at a high incidence. If bleeding events could be reduced with the withdrawal of antiplatelet therapy from the antithrombotic regimen with HM3, this could improve clinical outcomes for Medicare beneficiaries and have added relevancy to their treatment plan. For this purpose, it is important that Medicare beneficiaries are studied in this trial so that relevant outcomes may be translated more broadly.

To further characterize the portion of the subjects enrolled in the clinical investigation that display characteristics consistent with the Medicare population based on age, the clinical investigation results will be analyzed by age (< 65 years and ≥ 65 years) to ensure that the outcomes are similar between the Medicare and non-Medicare populations. Additional subgroup analyses are detailed in section 8.5.

5.4.2 Historically Under-Represented Demographic Subgroups

The Sponsor intends to implement the FDA's guidance on sex-specific data in medical device clinical investigations to ensure adequate representation of women and other traditionally under-represented demographic subgroups in this clinical investigation. As noted in the guidance, some barriers to participation of women and ethnic minorities in clinical investigations have traditionally been:

- Lack of understanding about main obstacles to participation of such subgroups in clinical research
- Inclusion/exclusion criteria potentially not needed to define the clinical investigation population may unintentionally exclude specific subgroups
- Under diagnosis of disease etiologies and pathophysiology leading to under referral of demographic subgroups
- Sex differences in disease etiology, which predispose one sex to LVAD therapy
- Avoidance of specific subgroups by investigators and Sponsors due to the perception that it takes more time and resources to recruit them
- Family responsibilities limiting women's ability to commit time for follow-up requirements

The Sponsor will take the following steps to ensure adequate representation of women and racial or ethnic minorities in this clinical investigation:

- All patients receiving an LVAD at enrolling sites will be considered for this study and this data will be reviewed regularly
- The Sponsor will provide training to investigational site personnel to ensure adequate representation of these demographic subgroups
- As appropriate and necessary, the Sponsor will retrain sites on the importance of recruiting and retaining subjects in the clinical investigation if trends in withdrawal or selection bias are noted
- The Sponsor will approach sites without bias or consideration for specific demographic subgroups
- The Sponsor will have informed consent materials in alternative languages and will work with sites and IRBs/ECs on recruitment materials

Clinical Investigation Plan

5.5 Subject Withdrawal

If a subject does not meet all inclusion criteria, or meets at least one exclusion criteria after the subject is enrolled (consented), but prior to randomization, the subject will be considered a screen failure and withdrawn and will not be included in the analysis populations.

Those enrolled (consented) subjects that meet all inclusion criteria and no exclusion criteria post implant will be randomized within 2-7 days post-implant (the day of implant is day 0). However, if these subjects do not meet the randomization eligibility criteria, are not randomized, never start the treatment arm regimen, experience a surgical event (≤ 14 days post implant) that requires investigator mandated anti-platelet therapy or experience an outcome ≤ 14 days post implant then they will be withdrawn.

Each randomized subject shall remain in the clinical investigation until completion of the required follow-up period; however, a subject's participation in any clinical investigation is voluntary and the subject has the right to withdraw at any time without penalty or loss of benefit. Conceivable reasons for discontinuation may include, but not be limited to, the following:

- Subject outcome including death, transplant, or device explant or exchange
- Physician or subject voluntary withdrawal
- Subject lost-to follow-up as described below.

The Sponsor must be notified of the reason(s) for subject discontinuation. The site will provide this information to the Sponsor. Investigators must also report this to their respective IRB/EC as defined by their institution's procedure(s).

No additional follow-up will be required or data recorded from subjects once withdrawn from the clinical investigation, except for the reason and status at the time of withdrawal (deceased/alive). Subjects withdrawn from the study will cease treatment arm medication and be transitioned to an anticoagulation regimen in accordance with site standard of care by the investigator.

In case of subject withdrawal of consent, the site should make attempts to schedule the subject for a final clinical investigation visit. At this final follow-up visit, the following will be recorded, with the subject's permission:

- Subject status (deceased/alive)
- Any adverse event details prior to withdrawal of consent

Lost-to-Follow-up

If all attempts at contacting the subject have been exhausted, then the subject is considered lost-to-follow-up. Site personnel shall make all reasonable efforts to locate and communicate with the subject (and document these efforts in the source documents), including the following, at each contact time point:

- A minimum of two telephone calls on different days over the specified follow-up windows to contact the subject should be recorded in the source documentation, including date, time and initials of site personnel trying to make contact.
- If these attempts are unsuccessful, a letter (certified, if applicable) should be sent to the subject.

Clinical Investigation Plan

- If a subject misses one or more non-consecutive follow-up contact time points, it will be considered a missed visit. The subject may then return for subsequent visits.

Note: Telephone contact with General Practitioner, non-clinical investigation cardiologist or relative without the presence of the subject or indirect documentation obtained via discharge letters will not be considered as subject contact.

Sites should attempt to retrieve unused portions of the treatment arm medication in subjects lost-to-follow, which should be returned to ALMAC Clinical Services per section 2.4.5.

5.5.1 Incidental Use of Aspirin Containing Products

At baseline and at each scheduled visit, subjects should be provided with the Sponsor provided list of aspirin containing products. At each visit post-implant, subjects should be asked if they have taken or been prescribed (by non-study physicians) any of the medications containing aspirin or aspirin-like compounds and, if so for what duration. Responses will be captured in the EDC. If a subject reports or other evidence of incidental aspirin use is obtained (i.e. a prescription which the patient confirms from a non-investigator healthcare provider) lasting for a duration of > 7 days, the subject will be withdrawn from the study.

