5.6 Transition to Open Label

During a subject's clinical course, post-randomization events may result in the investigator mandating antiplatelet therapy. The mandate may consist of the presence of an antiplatelet or the absence of all antiplatelets from the patient's antithrombotic regimen in response to clinical events. These subjects should remain in the study for the full 12-month study follow up whenever possible. Investigators may cease administration of the treatment arm medication for up to 72 hours without transitioning the subject to open label. In these instances, the treatment arm medication is no-longer administered, and investigator initiates their mandated therapy. If the cessation extends beyond 72 hours, these subjects are considered to have transitioned to open label and may not resume the treatment arm medication after transition.

Transition to open label does not constitute unblinding. Investigators will not know which randomized treatment arm patients who transition to open label were initially allocated. Study blinding will continue in patients transitioned to open label.

Clinical events which resulted in the transition to open label will be documented in the EDC. Subjects who transition to open label after 12 months will be considered to have completed the study required follow up at 12 months post implant. Subjects who transition to open label after 12-months of study follow up will be considered to have completed study follow up at that time except if a subject has experienced a stroke or potential stroke neurologic adverse event prior to transitioning to open label, then they will be followed for an additional 60-days post event for MRS score evaluation. In this case, the subject is considered to have reached end of study follow up upon completion of the MRS evaluation.

Clinical Investigation Plan

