6.8.1 Continued follow up beyond 12-months post implant

Subjects on the treatment arm medication will be followed every six months after the 12-month follow up visit until the final ongoing subject reaches the 12 month visit or experiences a study outcome. Only treatment arm medication details, subject status (including death, withdrawal, or transplant) along with adverse events and device deficiencies will be collected along with additional supportive data should adverse events or device deficiencies occur. If a patient's clinical course after 12 months of follow up requires transition to open-label, the patient will be considered to have reached the end of study follow up unless the transition to open label is due to a stroke, in which case the patient should be followed for an additional 60-days to capture the MRS score. The clinical reason for transition to open-label will be captured. Subjects transitioned to open label prior to 12 months of follow up should be followed to their 12-month follow up.

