6.9.4 Outcomes

Subjects will be followed for at least 12 months and until the final ongoing subject reaches their 12 month visit or an outcome is reached, whichever occurs first. Outcomes include death, heart transplantation, device explant, and withdrawal from the study. Outcomes must be reported to the Sponsor through the EDC system immediately upon discovery of the event. Subjects should continue follow up through 12-months whenever possible, even in the instance the subject has transitioned to open-label (e.g. due to pump thrombosis the investigator believes the patient should remain on open-label aspirin therapy).

If a subject receives a pump exchange during the follow-up period, this event will be considered a device explant outcome and data will be collected on the pump exchange procedure but not after. If a subject has a device explanted for suspected or confirmed pump thrombosis, the pump will be returned to the Sponsor for analysis. Standard commercial processes will be used for pump return.

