Primary Endpoint Evaluation	The primary endpoint composite success rate will be calculated for each treatment arm based on the number of subjects who survive to 12 months with no primary endpoint events divided by the total number of subjects in the Modified Intention to Treat Population (mITT) population. The placebo arm will be considered non-inferior to the aspirin arm if the lower boundary of the one-sided 97.5% confidence limit of the risk difference in the composite success between treatment arms (Placebo-arm minus Aspirin-arm) is greater than the non-inferiority margin (10%).
Number of Subjects Required for Inclusion in Clinical Investigation	[REDACTED]
Secondary Endpoint	
• Non-surgical Major Hemorrhagic Events• Non-surgical Major Thrombotic Events• Survival• Stroke Rates,• Pump Thrombosis Rates• Bleeding Rates, including:
○ Non-surgical Bleeding○ Moderate Bleeding○ Severe Bleeding○ Fatal Bleeding○ GI Bleeding
Descriptive Endpoints	Hemocompatibility Score, Rehospitalizations, Economic Cost Implications

Clinical Investigation Plan

Subject Follow-up	
- Baseline- Implant- Randomization- Discharge- Week 1 ± 3 days- Month 1 ± 7 days- Month 3 ± 30 days- Month 6 ± 30 days- Month 9 ± 30 days- Month 12 ± 30 days- Every 6 month ± 60 days until last subject has completed the 12-month follow-up.
Inclusion Criteria	
• Subject will receive the HeartMate 3 per standard of care (SOC) in accordance with the approved indications for use in the country of implant.• Subject will receive the HeartMate 3 as their first durable VAD.• Subject must provide written informed consent prior to any clinical investigation related procedure.• In patients of child bearing capability, not currently pregnant and on appropriate contraception.

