1.3 Clinical Investigation Design

This is a prospective, randomized, double-blinded, placebo-controlled clinical investigation of advanced heart failure patients treated with the HM3 with two different antithrombotic regimens: vitamin K antagonist with aspirin vs vitamin K antagonist with placebo. [REDACTED]

The clinical investigation has been designed to involve as little pain, discomfort, fear, and any other foreseeable risk as possible for subjects.

The clinical investigation will be conducted at up to 50 centers worldwide. The primary, and secondary endpoints will be evaluated as described in this SAP. Outcomes for this study include death, transplant, withdrawal or pump exchange. All subjects, site, Clinical Events Committee (CEC), and sponsor personnel, will remain blinded to the randomization scheme until the last ongoing study subject completes follow-up (specifically, experiences an outcome or reaches 12-months of follow up) and all data have been collected and adjudicated, exceptions will be justified in the study blinding plan (eg. DSMB). After a patient reaches 12-months of follow up, they will continue to be followed every 6-months, as long as they remain on the treatment arm medication, until the last ongoing patient reaches 12-months of follow up. Beginning at the 12-month follow-up visit, patients should be requisitioned two bottles of the treatment arm medication to cover the 6 months until the next follow up visit.

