2.3 Endpoint Analysis

2.3.1 Primary Endpoint

The primary endpoint is a composite of survival free of any non-surgical¹ major hemocompatibility related adverse event² at 1-year post implant.

¹ - Non-surgical – any event occurring > 14-days post implant.

² - Major Hemocompatibility Related Adverse Event:

- Stroke
- Pump Thrombosis (suspected or confirmed)
- Bleeding (including intracranial bleeds that do not meet the stroke definition)
- Arterial Peripheral Thromboembolism

A subject will be considered a success if they survive to their 12 month visit and have not experienced a non-surgical hemocompatibility related adverse events. Subjects who have an outcome (e.g. transplanted or explanted due to recovery) prior to their 12 month visit that have not reported a non-surgical hemocompatibility related adverse event prior to censoring will also be considered a success.

A subject will be considered a failure if:

- the subject expires prior to their 12 month visit
- the subject experiences a non-surgical hemocompatibility related adverse event prior to their 12 month visit.

The primary analysis will be performed using the mITT population.

[REDACTED]

[REDACTED]

[REDACTED]

[REDACTED]

Statistical Analysis Plan

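### More than 7 days of incidental aspirin ends data collection, while investigator-mandated open-label therapy does not: an avoidable gap in 12-month endpoint status, with bias of unknown direction

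*Protocol*

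**What the plan says.** Protocol 5.5.1 has sites ask at each post-implant visit about aspirin-containing products. If incidental use is found "lasting for a duration of > 7 days, the subject will be withdrawn from the study". The general rule in Protocol 5.5 then applies: "No additional follow-up will be required or data recorded from subjects once withdrawn from the clinical investigation", apart from the reason and whether the subject was alive at that time. No exception is made for withdrawals under 5.5.1.

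Subjects for whom the investigator mandates the presence or absence of an antiplatelet are handled differently. Protocol 5.6 states: "These subjects should remain in the study for the full 12-month study follow up whenever possible". Protocol 6.8.1 repeats it: "Subjects transitioned to open label prior to 12 months of follow up should be followed to their 12-month follow up". Protocol 6.9.4 says it a third time, "Subjects should continue follow up through 12-months whenever possible, even in the instance the subject has transitioned to open-label", and gives open-label aspirin after pump thrombosis as its example.

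On scoring, the success rate in Protocol Appendix VIII is the "number of subjects who survive to 12 months with no primary endpoint events divided by the total number of subjects" in the mITT population. SAP 2.3.1 counts as successes "Subjects who have an outcome (e.g. transplanted or explanted due to recovery) prior to their 12 month visit" if they had no qualifying event before censoring. SAP 1.3 says: "Outcomes for this study include death, transplant, withdrawal or pump exchange". The sections on missing data, analysis methods and the detailed population definitions are redacted.

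**The concern.** Both routes take a subject off the assigned regimen, yet one keeps the endpoint data and the other discards them. The primary endpoint is event-free survival at 1 year. A subject withdrawn event-free under 5.5.1 before month 12 has no observed 12-month status, and the cause is a post-randomisation exposure to one of the two treatments being compared.

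The rule does little to prevent contamination. Use is found mainly by asking at visits, which are three months apart from month 3 to month 12, so the exposure has usually happened by the time the subject is withdrawn. What the rule removes is the follow-up after it.

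The loss may be informative. Transient ischaemic attack and myocardial infarction are defined adverse events in Protocol Appendix II but lie outside the primary composite in Protocol 4.1. Either could prompt an outside aspirin prescription, and so withdrawal, before any stroke, bleed or death. An ITT analysis needs the later data, as do the secondary analyses that SAP 2.3.2 extends past transition to open label. For these subjects the data will not exist.

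**Working it through.** **1. Inputs.** From the documents: 628 randomised (Protocol 5.7), 1:1 (Protocol 3.0), so 628/2 = 314 per arm; margin 10 points, one-sided 97.5% limit (Protocol Appendix VIII). The assumed success rates, power and dropout are redacted, so 628 can be neither reproduced nor refuted. Nothing below tests it. Not in the documents, and therefore assumed: the fraction *w* of an arm withdrawn event-free under 5.5.1, and the probability *q* that such a subject would have failed by month 12.

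**2. Who is affected.** Adverse events are collected until withdrawal (Protocol 7.3.1), and outside medical records are requested with consent (Protocol 6.8). A subject with a qualifying event after day 14 is already a failure under SAP 2.3.1. Only subjects event-free at withdrawal lose their endpoint status.

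**3. How they are scored.** Appendix VIII, read literally, keeps such a subject in the denominator but not the numerator: a non-success. SAP 1.3 lists withdrawal as an outcome, and SAP 2.3.1 scores an event-free early outcome as a success, although its examples are transplant and explant for recovery. The public text does not settle it.

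**4. How much is undetermined.** Let S be the observed successes in each arm, and x the unknown successes among those withdrawn, with 0 ≤ x ≤ 314*w*. The 12-month difference (placebo minus aspirin) is (S_P + x_P)/314 − (S_A + x_A)/314. With the same *w* in both arms it can lie anywhere within ±*w* of (S_P − S_A)/314.

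| *w* | subjects per arm | difference undetermined by up to |
|---|---|---|
| 1% | 0.01 × 314 = 3.1 | ±1 point |
| 2% | 0.02 × 314 = 6.3 | ±2 points |
| 5% | 0.05 × 314 = 15.7 | ±5 points |

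These are extreme bounds: every withdrawn subject fails in one arm and none in the other.

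**5. Direction.** Bias is the scored difference minus the true difference; positive favours non-inferiority.
- Scored as success: bias = w_P q_P − w_A q_A.
- Scored as non-success: bias = −w_P(1 − q_P) + w_A(1 − q_A).

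Unbalanced example, w_P = 5%, w_A = 1%, q = 0.3 to 0.5 in both arms: scored as success, 0.04 × q = +1.2 to +2.0 points; scored as non-success, −0.04 × (1 − q) = −2.8 to −2.0 points. If the aspirin arm loses more, both signs reverse.

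Balanced example at the margin, true success 0.70 versus 0.60, so q_A = 0.3 and q_P = 0.4. Scored as success, the bias is w × (0.4 − 0.3) = 0.1w. Scored as non-success, it is −0.6w + 0.7w = 0.1w. Either way it is 0.1 point at w = 1% and 0.5 point at w = 5%. With the normal approximation at 314 per arm, one-sided type I error moves from 2.5% to 2.7% (w = 1%), 2.8% (2%) and 3.4% (5%) under either scoring, if all their events go unseen.

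**6. If they are excluded instead.** With 0.70 success in both arms, power at 314 per arm is 78.1%; it becomes 77.7% (w = 1%), 77.2% (2%) and 76.0% (5%).

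**The case against.** The strongest defence is that little is lost. The composite counts the first event, and outside aspirin prescribed after a stroke, pump thrombosis or arterial embolism beyond day 14 finds a subject who has already failed. Double blinding makes arm-related prescribing less likely. The aspirin-product list, the 7-day tolerance and the ban on added antiplatelets (Protocol 6.1) should keep numbers low. The two routes also differ: open label follows a clinical event and study capsules stop, whereas incidental use may occur while blinded capsules continue. Most of this stands, and it limits the size. It does not explain why follow-up should end, and it leaves prescriptions prompted by events outside the composite.

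A reader might infer that the rule hides placebo-arm failures and so favours non-inferiority. The documents do not support that. It needs losses concentrated in the placebo arm and scored as successes; Appendix VIII read literally scores them the other way, and the missing-data section is redacted. That redaction is not a fault in the plan. A shift worked out by placing every loss in the placebo arm and counting it as a success would be one scenario, not an estimate.

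**Conclusion.** The asymmetry is in the current text and is certain. It leaves 12-month endpoint status unobserved for subjects who are event-free when withdrawn under 5.5.1, for an avoidable reason. The direction of any bias is unknown, and its size rests wholly on an assumed withdrawal fraction. At 1% to 5% per arm the difference is undetermined by up to ±1 to ±5 points against the 10-point margin. Balanced loss produces only a small dilution, 0.1 to 0.5 point at the margin in the example worked; unbalanced loss matters more and can go either way. If incidental use proves rare, the practical effect is small. The point is worth acting on because data not collected cannot be recovered at the analysis stage.

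**What to change.** Amend Protocol 5.5.1, with a matching exception in 5.5, so that leaving randomised treatment is separate from leaving the study. Subjects with more than 7 days of incidental aspirin would stay in follow-up to month 12, with all endpoint events and vital status collected and aspirin start and stop dates recorded. On-assignment analyses may end at first incidental use.

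The amendment should cover follow-up and data collection only. The wording that study medication ceases is tied to withdrawal in 5.5, and a bare cross-reference to 5.6 would import its bar on resuming study medication. The sponsor must therefore reconcile 5.5, 5.5.1 and 5.6 on study medication for these subjects; no clinical rule is proposed here. The sponsor should also confirm that Appendix VIII, SAP 1.3 and SAP 2.3.1 agree on how an event-free withdrawal is scored.

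Cost: a short amendment with IRB/EC approval across up to 50 sites, and visits that were already scheduled. Some contaminated follow-up enters the treatment-policy analysis, which can dilute a difference in a non-inferiority comparison, so the on-assignment analysis should be reported beside it.
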